5.5 Study Evaluations

Visit 1 (Baseline assessment). This visit will most often occur directly after informed consent has been obtained (described above). The baseline assessments and prescribing provider referral form will serve to establish the patient's eligibility. Patient-reported outcome measures (PROMs) will be collected using tablet devices/paper/or interview and entered into the Behavioral Health Lab (BHL) software based on availability of a tablet device. Responses will be populated directly to CPRS/VISTA using the VA-approved BHL software. For eligible patients, a cheek swab will be taken for the commercial genetic test and several blood samples will be taken as described below. The patient themselves or the research coordinator will collect the cheek swab, based on patient preference. Blood will be collected as part of the discovery and secondary aims as described below. Patients who consent to the optional actigraphy component (see below) will be assigned an ActiGraph device and shown how to use it, including optional syncing. Providers will record the medication that they plan to prescribe for the patient prior to randomization and rate their expectancy for treatment outcomes. After data collection and the establishment of eligibility, the patient will be randomized to the intervention group or the delayed results group. Patient/provider dyads assigned to the delayed results arm will initiate therapy with the antidepressant that the patient and provider agreed upon prior to randomization. Patients in the intervention group will have their cheek swab sample shipped for testing, with the results, in most cases, returned to the site in 2-3 business days, Prescribing will then proceed; prescribers will be encouraged to use the genetic test results in selecting a medication. Occasionally shipping delays or the need for further sample testing may delay the results for up to four additional business days. If delays are identified, and the report will not be available within the expected three business days, the local site will notify the provider that the report has been delayed and provide an updated timeframe. The provider has the option to wait until the report is available or to proceed with prescribing without the genetic results. Visit 1 alternate. When a face to face visit is not possible, we will use an alternate virtual process for visit 1. If the subject is reached and consents to the study, the baseline assessments will be completed. If eligible, a PGx cheek swab kit will be sent to the patient via UPS and the subject will be provided instructions on collecting the sample and returning by FedEx to Assurex. These instructions will also include directions to contact their primary care provider before returning the sample if they have felt any new physical symptoms of COVID-19, including loss of taste. We will also include in this package an Information Sheet with a summary of the study including consent elements and contact information. Study staff will check UPS tracking information daily to confirm that this package is received by the subject. Study staff will also schedule a call back time with the subject when the package is expected to arrive, to walk the subject through sample collection and shipping. We intend to make this process as easy as possible for the Veteran, assisting them with scheduling a FedEx pick-up at their home or providing them with the location of local FedEx drop boxes Once the sample return is registered in the FedEx system, the Veteran will be randomized, and the provider and patient will be informed of the study arm. To encourage return of samples, participants will be compensated \$25 for sample receipt. If the sample is not registered in the FedEx system within 10 business days of referral, the provider will be notified by the study staff so that they can determine whether to return to usual care or to continue. Blood draws are not included in this virtual visit.

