 - a. Treatment decision. At the time of recruitment, the provider will be asked to record the antidepressant that he or she would prescribe if no genetic test information were available. This will be used to measure whether the provider/patient dyads in the intervention group will use fewer medications that have potential gene-drug interactions based on commercial PGx test results than dyads in the delayed results group (Hypothesis #2). The provider will also rate the likelihood that the antidepressant will be effective for the patient, the patient's anticipated degree of adherence, and how helpful the provider believes the PGx results will be in informing care for the patient.
 - b. Confirmation of inclusion and intent to prescribe. The referral form requests that the provider confirm the lack of serious psychiatric illness, the need for urgent treatment, and the intent to prescribe monotherapy. If we later find by administrative data that an exclusionary diagnosis has been used on a patient, this will not be considered a protocol deviation as chart extraction is not the method of confirming the exclusionary diagnoses.
- d) Provider Focus groups. We will ask a subset of the sites to participate in virtual focus group interviews. We will conduct up to ten 45 minute-long (15-minute presentation, 30-minute discussion) focus groups with at least 3-5 primary care providers and/or 3-5 psychiatrists (and other specialty mental health providers) in each group. The focus groups will include a brief presentation on PGxs, including an Assurex sample report of results, and discussion about current knowledge and perceptions of PGx testing. They will provide feedback on how PGx results should be returned to providers and patients, and input on overcoming implementation barriers. All groups will be held virtually via Lync On-Line Meetings so that slides can be presented. The site PIs will encourage participation and their research coordinators will coordinate the meeting arrangements. Providers will provide written informed consent prior to participation. One consent form will serve for all components of provider

participation. The focus groups will also be recorded and professionally transcribed for detailed review. Study staff will also take notes.

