5.6.b. Patient and provider use of PGx results (Hypothesis #2). For each provider-patient dyad in the trial, we will use the results of the genetic test to classify each medication prescribed by the provider to that patient as green, yellow, or red, thus creating an ordinal measure for each time the provider prescribes a medication. Our primary response for Hypothesis #2 will be the correspondence between the study-period prescription for the provider-patient dyad across the randomized groups. We will compare the groups on the probability of receiving medications of the three types (red, yellow, green) using mixed effects ordinal regression model, including random intercepts for providers.

5.6.c. Secondary Responses (Hypothesis #3). We will use generalized linear regression models to evaluate secondary outcomes, using the same covariates as above: a binary indicator for intervention group, and variables for site, provider, and depression severity. Regression models will include random effects to accommodate correlations due to repeated measures and nesting of patients within providers.

Secondary analyses will include an examination of the longitudinal trajectories of PHQ-9 summaries of depression severity across the intervention phase. These models will use the overall PHQ-9 score as a response, yielding a set of continuous (possibly skewed) repeated measures. These responses will be analyzed using mixed-effects linear models (or mixed-effects gamma models, depending on the degree of skewness). We will compare the groups on functional improvement, using the mental health component of the VR-12 score, with analogous generalized linear mixed effects models appropriate to the response distribution.

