- 4) In the delayed results group, there will be a decrease in the probabilities of antidepressants characterized as red or yellow prescribed in the 30 days after the release of the PGx test results, compared to the 30 days prior to release of results.

Rationale for amendments made– To clarify the intent of Hypothesis #4, it was agreed that this analysis would not be included in the primary paper.

Sample Size and Power Considerations.

We have two primary hypotheses, so we will test each at a 2.5% significance level, using two-sided tests.

The primary outcome for Hypothesis #1 is a set of repeated binary indicators of remission from depression. We assume a 20% loss to followup, distributed evenly over time, and across the two groups. The anticipated remission rate in usual care is based on results from STAR*D [2]. For the base rate, we consider rates of 20-25-30-35%, and for the treatment effect, we look at effects of about 5%. To account for correlations between the results for two patients of the same provider, we assume an intra-class correlation (ICC) of 0.05 or lower for providers, which should also address the nesting within sites [21]. We assume our design will have approximately 200 providers, with an average of ten patients per provider, so the design effect for an ICC of 0.05 is 1.45. For a base rate of 30% (based on results from STAR*D [2]), and an assumed within-patient correlation of 0.4 or lower in a compound symmetry structure, we have 82% power for a 5% treatment effect and 92% power for the same effect in an autoregressive (ar(1)) structure, with higher power for the same 5% effect with lower base rates. For a provider ICC of 0.01, where we have an effective sample size of 1835, we have power in excess of 90% for 5% effects, under either covariance structure.

For Hypothesis #2, the primary outcome is an ordinal response indicating the gene-drug interaction potential (coded as green, yellow, and red based on the PGx test for non, moderate and significant drug- gene interactions) of the initial prescription made during the intervention period. Assuming that the overall proportions in the sample are approximately 40%/40%/20% for green/yellow/red, respectively, then our sample of 2000 provides 80% power to detect a common odds ratio of 1.29 under a proportional odds model, at a significance level of 2.5%.

Data Analysis Plan for the Completed Sample.

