Prior to performing analyses, we will apply standard data-cleaning procedures. Specifically, we (1) screen the data for data-entry errors, (2) check for outliers, (3) assess the extent and pattern of missing data, and (4) check that appropriate assumptions of normality for data distributions are met whenever necessary.

Primary hypotheses.

Patient response to treatment (Hypothesis #1). The primary outcome measures will be a set of binary indicators of remission (PHQ-9 score ≤ 5) across the intervention phase time points (weeks 4, 8, 12, 18, and 24). We will use a mixed-effects logistic regression model to test the hypothesis that patients whose treatment is informed by the PGx results are more likely to be in remission than those receiving usual care. The model will have a binary indicator of intervention group as the main explanatory variable, together with the baseline phq-9 score, and variables for time and group-by-time effects, and a fixed effect for site. To accommodate nesting of repeated measures within patients, and nesting of patients within providers, the models will include a random intercept for provider and correlated residuals within patient; we will use information-criteria comparisons to compare the fit of different covariance structures to ensure adequate fit. As there is particular interest in the remission rate of patients at the end of treatment, we will report on a comparison between the groups at the endpoint of the intervention phase (week 24), based on our final model.

Patient and provider use of PGx results (Hypothesis #2). For each provider-patient dyad in the trial, we will use the results of the PGx battery to classify each antidepressant medication prescribed by the provider to that patient during the study period as green, yellow, or red, thus creating an ordinal measure for each time the provider prescribes a medication. The primary outcome for Hypothesis #2 will be the ordinal variable corresponding to prescriptions written in the first 30 days after randomization. In the case of Veterans having simultaneous prescriptions, we will use a “worst-case” approach, assigning the highest level of the green, yellow and red scale. We will compare the groups on their probabilities of prescriptions of green, yellow, or red using a mixed-effects ordinal regression model, including random intercepts for providers and fixed effects for sites.

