Rationale for amendments made– The study design has limited control on the number of providers recruited per site, or the number of Veterans treated per provider. In settings where these numbers vary considerably over sites and providers, there can be considerable challenges in fitting mixed effects models that take detailed account of the correlations within Veterans, providers, and sites. If necessary, we will adjust some aspects of the model specification above in order to fit the models.

In supplementary analyses, we will include some covariates in the analyses described above, to examine the effects of certain patient-level and provider-level characteristics. These comprise of age, race, gender, presence and severity of PTSD, and provider-level location of care (primary care vs mental health outpatient). To examine heterogeneity of effect, we will also include interactions between these variables and the intervention variable.

Rationale for amendments made– Based on prior literature showing that the PGx test results may only apply to 10-20% of the randomized population, we will use the PGx test information to define a “genetic susceptibility” variable for each participant. The susceptibility variable will correspond to the proportion of antidepressant medications that are “red” for each Veteran. This is in essence a marker of genetic risk for having gene-drug interactions. We will use this variable as a Veteran-level covariate in reruns of the primary analyses. This change was added as more thought was given to results from studies released after the start of the trial and in consideration of genotype prevalence.

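### The Hypothesis #2 analysis leaves out the pre-randomisation intended antidepressant that the protocol collects for that hypothesis, and so gives up precision on a primary test

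*SAP*

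**What the plan says.** Protocol 5.5, Visit 1: "Providers will record the medication that they plan to prescribe for the patient prior to randomization". The referral-form description in 5.5.a gives the content of the record: "the provider will be asked to record the antidepressant that he or she would prescribe if no genetic test information were available". It also gives the purpose, naming Hypothesis #2: "This will be used to measure whether the provider/patient dyads in the intervention group will use fewer medications that have potential gene-drug interactions". It does not say how the record enters the analysis.

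Neither analysis section takes it up. Protocol 5.6.b specifies a "mixed effects ordinal regression model, including random intercepts for providers". The SAP's Hypothesis #2 paragraph compares the arms "using a mixed-effects ordinal regression model, including random intercepts for providers and fixed effects for sites". The SAP's supplementary covariates are age, race, gender, PTSD and location of care. The SAP also defines a genetic susceptibility variable, the share of antidepressants that are red for the patient, and says: "We will use this variable as a Veteran-level covariate in reruns of the primary analyses". The SAP section on missing data plans multiple imputation for Hypothesis #2 without naming predictors.

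On power, the SAP states that "our sample of 2000 provides 80% power to detect a common odds ratio of 1.29 under a proportional odds model", at 2.5% two-sided and with overall proportions of 40/40/20.

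**The concern.** The outcome is the colour of what was prescribed in the first 30 days. The intended drug can be coloured from the same test result in both arms, and it is fixed before allocation. It should predict the outcome well in the delayed arm, because Protocol 5.5 says those dyads start the drug agreed before randomisation.

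The susceptibility variable is no substitute. It depends on genotype alone, ignores which drug was planned, and enters only when the analyses are rerun. The SAP adjusts the other primary hypothesis for its baseline measure and gives no reason for treating this one differently.

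At stake is precision on one of two primary hypotheses, tested at 2.5% with a fixed sample. The protocol also gives the variable a purpose that no analysis carries out.

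**Working it through.** **1. The plan's own figure.** Inputs from the SAP's power section: N = 2000, proportions 0.40/0.40/0.20, OR 1.29, two-sided α = 0.025. Allocation of 1:1 is assumed because the ratio is not stated. The proportional-odds (Whitehead) formula gives:

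- V = (N/12)(1 − Σp³) = (2000/12)(1 − 0.064 − 0.064 − 0.008) = 144, so √V = 12.
- Power = Φ(ln 1.29 × 12 − 2.241) = Φ(3.056 − 2.241) = 79.2%.
- N for 80% power is 2036, within 3% of 2000.

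The stated 80% therefore reproduces, as the power of an analysis without a baseline covariate.

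**2. Simulation set-up.** There were 2000 patients under 200 providers of 10, with provider ICC 0.05 on the latent scale and 1:1 allocation within provider. Marginal probabilities solving OR 1.29 with 40/40/20 overall were 36.9/41.0/22.0% (delayed) and 43.1/39.0/18.0% (intervention). Two rates are assumptions:

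- *c*: the probability that a delayed-arm outcome carries over the intended colour; otherwise the colour is redrawn. Values 0.9, 0.7, 0.5 and 0.3 give colour agreement of 94, 81, 68 and 56%. Second drugs and switches count in 1 − c.
- *f*: the share of intervention dyads choosing independently of the intended drug. The rest follow the delayed-arm process and are then shifted so that the marginal OR stays at 1.29.

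The test is the arm difference in mean ridit, either unadjusted or standardised over intended colour: Δ = Σₓ p(x)[mean ridit in the intervention arm at x − mean ridit in the delayed arm at x], with x the intended colour and p(x) pooled over arms. The standard error is provider-clustered and influence-function based. There were 2500 runs per scenario.

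**3. Power.** Unadjusted power was 79–83% across runs. Standardised power was:

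| c | f = 0 | f = 0.5 | f = 1 |
|---|---|---|---|
| 0.9 | 100% | 97% | 88% |
| 0.7 | 97% | 92% | 85% |
| 0.5 | 89% | 86% | 83% |
| 0.3 | 85% | 81% | 82% |

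The variance of the arm effect falls to 0.29–0.97 of the unadjusted value. At c = 0.7, f = 0.5 the ratio is 0.75; since √0.75 = 0.87, the interval is about 13% narrower.

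**4. Hand check, ignoring clustering.** Carry-over with probability c gives a correlation of about c between intended and actual scores in the delayed arm, and about c(1 − f) in the intervention arm. With equal allocation and arm-specific slopes, the variance ratio is about VR = 1 − [(ρ₀ + ρ₁)/2]², and power is Φ(3.056/√VR − 2.241).

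- c = 0.7, f = 0.5: VR = 1 − 0.525² = 0.724; power = Φ(1.35) = 91%.
- c = 0.9, f = 1: VR = 1 − 0.45² = 0.798; power = Φ(1.18) = 88%.
- c = 0.3, f = 1: VR = 1 − 0.15² = 0.978; power = Φ(0.85) = 80%.

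These agree with the table to within about 2 points.

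**5. A second simulation** without provider effects added intended colour as a plain covariate, under two different mechanisms. At 70% colour agreement, adjusted power was 87% and 98%. At chance agreement (36%) it was 79–80%.

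**6. Type I error (nominal 2.5%).** The standardised test rejected 2.4–3.2% of the time, and the unadjusted test with the same kind of standard error 2.2–3.1% (5000 null runs). The conditional proportional-odds likelihood-ratio test rejected 0.6% (c = 0.9, f = 0), 1.9% (c = 0.7, f = 0.5) and 2.9% (c = 0.9, f = 1). Plain cluster-robust regression errors with arm-by-colour terms rejected 3.8–4.4% at c = 0.9 with f = 0.5–1. The form of adjustment therefore matters.

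**The case against.** The planned test is valid and its power statement is right, so this could be called an optional refinement. Four points deserve weight.

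- **It is more than one extra term.** The simplest change, a covariate in the ordinal model, is not well calibrated, and it moves the target from a marginal OR of 1.29 to a conditional one (1.35–1.53 at 70% agreement). The better version changes the primary test to standardised probabilities. This stands as a real cost. Standardisation does, however, stay with the SAP's stated aim of comparing the arms' probabilities of each colour.
- **The gain rests on two unknown rates.** The 21-point figure needs c = 0.9 and no intervention dyad choosing afresh, which is unlikely when providers are encouraged to use the report. Agreement is also lowered by Protocol 5.2, which lets delayed-arm dyads start a drug of their choosing, and by the SAP's rule of scoring the worst colour among simultaneous prescriptions. This stands, and it is why a range is given.
- **Power is judged only at the detectable effect.** By the step 1 formula, unadjusted power is already about 96% at OR 1.4 and 99.6% at OR 1.5. There the benefit is a narrower interval rather than power.
- **Feasibility was not tested.** The SAP warns that uneven numbers per provider and site may make the models hard to fit. The simulations used equal provider sizes, no site effects and no missing prescriptions. Some intended drugs may also have no colour on the test report.

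None of this explains why a record collected for Hypothesis #2 has no role in its analysis.

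**Conclusion.** The concern holds. The protocol assigns the pre-randomisation intended drug to Hypothesis #2, and neither the protocol's nor the SAP's analysis uses it. The consequence is lost efficiency, with no bias and no error in the stated power. At the SAP's design the loss is about 1 to 21 percentage points of power; at c = 0.7 adjusted power is 85–97%. If agreement is low (c = 0.3) the gain is only 1–3 points. No scenario run showed a loss of power. The size rests on the assumed c and f, 1:1 allocation, equal provider sizes, and no site effects or missing prescriptions. The change should be made, with medium confidence in how much it gains.

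**What to change.** Before outcomes are examined by arm, amend the SAP's Hypothesis #2 section as follows:

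- Add the colour of the referral-form antidepressant, taken from the patient's own test, as a three-level baseline covariate. State how an unrecorded drug, or one with no colour on the report, is handled.
- Let its effect differ by arm, and base the test on the arm probabilities of green, yellow and red standardised over it.
- Use provider-clustered robust standard errors that also allow for averaging over the covariate. Do not rely on the conditional proportional-odds test alone; report any conditional odds ratio beside the standardised probabilities.
- Name intended colour among the predictors in the Hypothesis #2 imputation model.
- Keep the analysis without the covariate as a sensitivity analysis.

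If the sponsor prefers the present model, the SAP should say why the record is not used, so that it agrees with Protocol 5.5.a.

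The cost is SAP wording, a standardisation step and a few more terms in a model that may already be hard to fit. No new data are needed.

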Randomization. We will randomize patients to the intervention or delayed results arms, controlling for possible bias due to confounding by provider by using a within-provider randomization scheme within each site. Overall, this scheme will balance treatment conditions across known (e.g., primary care versus specialty care) and unknown (e.g., future adherent versus non-adherent status at randomization) provider characteristics. In addition, as we expect the depression severity of patients to be associated with primary versus specialty care status of the providers, stratification will also tend to balance depression severity across the intervention groups. The randomization will be based on a permuted blocks approach, with (slightly) varying block sizes to discourage "guessing" of upcoming allocations [38]. The research coordinator at each site will conduct the randomization, having been trained on the use of the system during the study initiation meeting. Within each site, the system will maintain a log of the participants randomized. Each site will also have a short list of random assignments, one list per consented provider, to be used in the event that there is a system failure at the time of randomization. The list of randomized allocations will be maintained separately from the tracking and research data, to ensure blinded assessments by the interviewers.

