5.6.a Patient response to treatment (Hypothesis #1). The primary outcome measures will be a set of binary indicators of remission (PHQ-9 score \leq 5) across the intervention phase time points (weeks 4, 8, 12, 18 and 24). We will use a mixed effects logistic regression model to test the hypothesis that patients whose treatment is informed by the PGx results are more likely to be in remission than those receiving usual care. The model will have a binary indicator from the intervention group as the main explanatory variable, together with variables for time and group by time effects. The model will also include a fixed effect for site. The covariance structure of the model will take the hierarchical structure of the design into account, to accommodate nesting of repeated measures within patients, and nesting of patients within providers. Including a random intercept for provider, and correlated residuals within patient, should account for the nesting, but we will use information criteria to compare the fit of different covariance structures to ensure adequate fit. As there is particular interest in the remission rate of patients at the end of treatment, we will report a model-based comparison between the groups at the endpoint of the intervention phase.

To examine the effects of patient-level and provider-level characteristics, we will include these variables and their interactions with intervention group in the logistic regression model. For example, we will examine the effects of sex, race and ethnicity, baseline depression severity, the number of prior treatment episodes, and the effects of primary care versus specialty care, etc. We will also test for heterogeneity of the intervention effect across sites (i.e., site by treatment interactions). Analyses to assess the influence of missing data, and of adherence at the provider and patient level, are described below. Our reports will include clear descriptions of the statistical methods used and the clinical interpretations of the parameters used to test the hypotheses, with estimates, standard errors, confidence intervals and *p*-values associated with the parameters.

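### Genetic susceptibility is added because the test may matter for only 10-20% of Veterans, but the SAP plans it only as a covariate and states no interaction with arm

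*SAP*

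**What the plan says.** The variable appears in the SAP's second amendment note after the primary hypotheses, in the data analysis plan. The reason is given first: "Based on prior literature showing that the PGx test results may only apply to 10-20% of the randomized population". The definition follows: "The susceptibility variable will correspond to the proportion of antidepressant medications that are" red for each Veteran, described as a marker of genetic risk for gene-drug interactions. Its use is one sentence: "We will use this variable as a Veteran-level covariate in reruns of the primary analyses".

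Interactions are planned elsewhere.

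- **SAP, supplementary analyses (the paragraph just before the note).** Five characteristics are listed: age, race, gender, PTSD and location of care. Then: "To examine heterogeneity of effect, we will also include interactions between these variables and the intervention variable". Susceptibility is not in that list.
- **Protocol 5.6.a (Hypothesis #1).** For patient and provider characteristics, "we will include these variables and their interactions with intervention group in the logistic regression model". The examples end in an open et cetera. None is genetic, and the sentence concerns the remission model only.

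The SAP's Hypothesis #1 model contains arm, baseline PHQ-9, "variables for time and group-by-time effects, and a fixed effect for site". On the last visit the SAP adds: "we will report on a comparison between the groups at the endpoint of the intervention phase (week 24), based on our final model".

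**The concern.** If the result can change prescribing for only a minority, any benefit should sit mainly in that minority. The useful question is then whether the arm effect grows with susceptibility. A main-effect covariate does not address it: the model still fits a single arm effect on its own scale for every level of susceptibility. Because susceptibility is fixed by genotype and arm is randomised, adjusting for it should barely move the arm estimate.

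As written, the rerun would therefore nearly repeat the primary result. If the overall effect is small, readers will ask whether Veterans with many red medications benefited, and an interaction fitted at that stage would be open to the charge of being post hoc.

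**Working it through.** The textual point needs no arithmetic. The calculations show what the covariate-only rerun would and would not reveal, and how precise an interaction would be. The plan gives no figure for this analysis to reproduce.

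**Inputs from the documents.** Base remission 30%, within-patient correlation 0.4 (compound symmetry), five visits, 20% loss spread evenly, N = 2000, and a provider design effect of 1.45, giving an effective N of 2000/1.45 = 1379.

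**Assumptions not in the documents.** Susceptibility is yes/no with share f = 10% or 20%; a gain b occurs only in that share; allocation is 1:1; the test is two-sided 5%.

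**1. What the covariate shows (f = 20%, b = 10 points).** Marginal remission is 30% against 0.30 + 0.20 × 0.10 = 32%. The arm odds ratio is (0.32/0.68)/(0.30/0.70) = 1.098. Adding the covariate leaves it at 1.098. With the interaction it is 1.000 in the rest and (0.40/0.60)/(0.30/0.70) = 1.556 in the susceptible. At f = 10% the arm odds ratio is 1.048 both ways.

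**2. Variance factor for the time-averaged effect.** A patient seen k times contributes information k/(1 + 0.4(k − 1)). With 4% lost before each visit, total information is 0.04 × (1 + 1.429 + 1.667 + 1.818) + 0.80 × 1.923 = 1.775, so the factor is 1/1.775 = 0.563. For week 24 alone it is 1/0.80 = 1.25.

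**3. Interaction power.** z = b / √(V_susceptible + V_rest), where each V is the variance of that group's arm difference. For N = 2000, f = 20%, b = 10 points:

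- V_susceptible = 0.563 × (0.21 + 0.24)/200 = 0.001267
- V_rest = 0.563 × (0.21 + 0.21)/800 = 0.000296
- z = 0.10/0.0395 = 2.53, giving power 72%

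| Analysis | N | 10-point gain, f = 10% / 20% | 15-point gain, f = 10% / 20% |
|---|---|---|---|
| Time-averaged | 1379 | 35% / 56% | 65% / 88% |
| Time-averaged | 2000 | 47% / 72% | 80% / 97% |
| Week 24 only | 2000 | 25% / 40% | 47% / 72% |

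**4. Which N applies.** Protocol 5.2 describes "controlling for possible bias due to confounding by provider by using a within-provider randomization scheme within each site", so the interaction is largely estimated within provider. A simulation of 200 providers with ten patients each, five per arm, ICC 0.05 and 20% loss gave 46% / 68% for 10 points and 81% / 95% for 15 points. N = 2000 therefore fits this design better than 1379.

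**5. Precision in the susceptible (b = 10 points).** The 95% half-width is 1.96 × √V_susceptible: 9.9 / 7.0 points at N = 2000 and 11.9 / 8.4 at 1379 (f = 10% / 20%).

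**6. Continuous susceptibility.** If the gain is proportional to susceptibility with mean g, then z = g × CV / SE(arm), where CV is the coefficient of variation of susceptibility. With g = 2 points and N = 2000, power is 25% at CV 1 and 73% at CV 2. The documents give no distribution.

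**7. Hypothesis #2.** Suppose the delayed arm has red probability S and yellow 40%, and prescribers in the intervention arm turn half of would-be red choices green for every patient. The fitted common odds ratio is 0.77 at S = 0.1, 0.60 at 0.2 and 0.375 at 0.4, although behaviour is identical throughout. At S = 0 red is impossible. Part of any interaction here is built into the scale.

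**The case against.** The strongest reply is about reading. Most amendment notes in this SAP annotate the text just above them, and this one follows the paragraph that adds covariates and then their interactions. It uses the same word, covariate, so it may simply add one more member to that set. Because the set applies to the analyses above it, Hypothesis #2 would be covered as well. A variable added by amendment would not be expected in the older list, and the protocol's list for Hypothesis #1 is open.

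This shows that an interaction may have been intended, and that much stands. It does not supply prespecification: the note states its own use and stops at the covariate, whereas the paragraph above takes the second step explicitly.

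It can also be said that the SAP never uses the term effect modification, and that susceptibility is a reasonable prognostic covariate, especially for Hypothesis #2. That is fair, and a reason to keep the covariate. But a concern that the test is relevant to only some of those randomised is about where the intervention can act, and a prognostic adjustment does not answer it.

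Finally, most figures assume a yes/no split when the variable is a proportion, and the share to whom the test applies is not the distribution of that proportion. In the Hypothesis #2 example at S = 0.1 the two cumulative odds ratios are about 0.47 and 0.82, so the common 0.77 averages over non-proportional odds. Both points stand. The figures are illustrations, and predicted probabilities are the better summary for Hypothesis #2.

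**Conclusion.** The concern holds, at minor severity. The SAP gives a reason that calls for a susceptibility-by-arm interaction and states only a covariate. On the natural reading, the planned rerun would leave the arm odds ratio essentially unchanged (1.10 and 1.10 in the illustration) while the two groups differ (1.00 and 1.56).

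Power for the interaction is limited unless the gain is large or the susceptible share is near the upper end of the quoted range. Small modification would probably be missed, and week 24 alone is weaker still. These sizes depend on the assumed split, gains and 5% level; the conclusion about the wording does not. Confidence is medium because an interaction may have been meant. The analysis is supplementary, so no primary conclusion is at risk.

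**What to change.** Keep the covariate rerun and add a paragraph to the SAP along these lines:

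> In exploratory supplementary reruns of the Hypothesis #1 and #2 models we will also include the interaction of susceptibility, kept continuous, with intervention group. These reruns make no claim on the 2.5% significance levels. For Hypothesis #1 we will report the arm effect with 95% CI at one low and one high value of susceptibility, fixed before unblinding from the pooled distribution with arm masked, both averaged over weeks 4-24 and at week 24. No three-way term with time is included, so modification is taken as constant over time on the logit scale. For Hypothesis #2 we will report arm differences in the predicted probabilities of green, yellow and red at non-zero values of susceptibility, and note that part of any interaction is mechanical. A non-significant interaction will not be read as evidence of a uniform effect.

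The same paragraph should state which antidepressants form the denominator of the proportion, since the SAP does not.

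The cost is this paragraph and one results table, with no new data. The drawback is one more heterogeneity analysis of limited power, so reporting should rest on the estimates and intervals.
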